3.0 Inclusion and Exclusion Criteria*

3.1 **Participant engagement will be referenced as "Pilot Cohort"** in this protocol.

PILOT COHORT Inclusion Criteria:

- Age \geq 18 years
- Patients diagnosed with an active cancer diagnosis, either undergoing active cancer treatment or receiving treatment for an advanced cancer or are receiving palliative care
- Treatment managed at participating clinic (DFCI outpatient palliative care, gastrointestinal cancer center, and DFCI satellite clinic Merrimack Valley or Londonderry)

- Chronic pain related to cancer or treatment (≥ pain score of 4)
- Has an active prescription for at least one opioid medication to treat their cancer pain (i.e. not for post-surgical pain)
- Own a compatible smartphone (android) or is willing to use an android device provided by the study team
- Completes baseline survey

Pilot Cohort Exclusion Criteria:

- Patients in survivorship: patients who have completed their treatment regimens, are not actively receiving treatment for an advanced cancer, or have a cancer that is in remission
- Cognitive impairment that would interfere with study participation, as judged by treating clinician
- Inability to speak English: the intervention has not yet been translated to Spanish
- History of opioid use disorders
- Enrolled in hospice
- Currently hospitalized
- Use of transmucosal fentanyl, given safety concerns and ongoing risk mitigation program required to prescribe these (TIRF REMS).
- Pain primarily related to a recent surgery
- 3.2 We will exclude adults who are unable to consent, individuals who are not yet adults (infants, children, teenagers), pregnant women, and prisoners.

4.0 Study-Wide Number of Subjects*

N/A

Please find the summary of study-wide number of subjects below:

Cohort	Maximum # of participants
Pilot Cohort	Up to 15 patients
Total accrual	Up to 15 participants

5.0 Study-Wide Recruitment Methods*

Recruitment methods are outlined for this Pilot Cohort in Reference section 21.

6.0 Multi-Site Research*

N/A

7.0 Study Timelines*

- 1. Describe: Patients in this Pilot Cohort will be in the research study for 6 weeks total including: a 4-week intervention period and 2-week post intervention period. Patients will use the app for a total of 4 weeks (4-week intervention period), and will complete surveys at baseline, 4 weeks (end of intervention period), and at 6 weeks (end of 2-week post intervention period).
 - We anticipate enrolling 1-2 patients per week during the pilot period, and should thus complete the study within 4-5 months.
 - 2. The study timeline may change due to unforeseen circumstances. The estimated date for the investigators to complete this study (complete primary analysis) is October 31, 2022.

8.0 Study Endpoints*

8.1 ENDPOINT 1: The primary objective is to determine feasibility and acceptability of STAMP+CBT. Specifically, we will evaluate patients' adherence to daily and weekly comprehensive symptom selfassessments within the STAMP+CBT app. We will calculate patients' overall adherence rate and 95% confidence interval. Defined using precision analysis, we will consider the intervention to be feasible if >70% of subjects complete >4 of the 6 pain-CBT modules and completes 50% of surveys by the end of 4 weeks (completion of the 4week intervention study period; completion of the 2-week post intervention period will be exploratory).^{40,41} The intervention will be considered **acceptable** if >80% of the acceptability items are rated 4 or higher/5; lower ratings will lead to app refinements. Other feasibility measures will assess time to accrual, participation rates, study retention and completion rates, and the number of patients who continue to review app content between weeks 5-6 (post-intervention period). Power calculation: With 10 patients, we will be able to estimate these proportions with margins of error (half of a 95% confidence interval) of approximately 18% or less assuming that the feasibility threshold of 70% is reached. This margin of error is small enough so that proportion estimates relevant to study feasibility will be

accurate and provide informative guidance for future, larger studies. Using **qualitative** framework analysis methods, we will explore barriers/facilitators, suggested changes to content, acceptability of intervention engagement, and whether app use continues after completion. Although power is not sufficient in this pilot, we will explore associations between levels of engagement and changes in pain severity/interference, opioid use, catastrophizing, sleep, mood, and pain self-efficacy.

8.2 COMPREHENSIVE ENDPOINT: The study team will use qualitative and quantitative results to determine the feasibility and acceptability of this pain CBT mobile health app for patients with cancer. This feasibility study will inform final modification to the application and study procedures in preparation for a future efficacy study of the STAMP+ CBT mobile health app.

9 Procedures Involved*

9.1 STUDY PROCEDURES:

The content for the STAMP+CBT application can be reviewed and referenced in appendices D, F, Y, Z. Once app programming is completely finalized, patients in the Pilot Cohort will engage in the pilot study to evaluate app feasibility and acceptability.

- 9.2 Patients in the Pilot Cohort will pilot the application for 4 weeks (or 6 weeks if they request to review the content further, this will allow us to test the correct length of app use). The onboarding and monitoring protocol is available in Appendix S. In addition, the RA will contact participants after 4 weeks (end of intervention period), and 6 weeks (end of 2-week post-intervention period). The purpose of these contacts would be to schedule the end of intervention interview and confirm completion of survey assessments, as well as the final survey assessments at 6 weeks (end of 2-week post-intervention period).
- 9.3 Participants will fall into only one eligibility category:

Pilot Cohort = Patient pilot testing

Description	Components of Participation
Participants will include DFCI patients presenting to outpatient palliative care, GCC, or satellite (MV and LD) clinics with ongoing chronic cancer pain management issues. Participants will meet with the study team in person, over the phone, or via a compliant and secure video chat/screen- share platform (i.e. Zoom). We will conduct the pilot cohort with up to 15 patients. Each participant will receive a \$25 gift card upon completion of the 4-week intervention period, and another \$25 gift card upon completion of the 2-week post intervention survey. The first 5 patients will onboard to the application and their involvement/feedback will focus on making final revisions onboarding for the application and study procedures. Therefore, the following 10 patients' data will be included for pilot study analysis and feasibility findings.	 Use the STAMP+CBT mobile app for 4 weeks (intervention period, 4 weeks for content introduction, extended 2 weeks for review of content if patient's request this) Engage with pain CBT content including a goal-setting module, relaxation exercises, and educational content Daily and weekly reporting of pain, catastrophizing, mood, and sleep symptoms and painkiller usage and satisfaction through the app (Appendix U) Complete survey assessments at baseline, 4 weeks (end of intervention period), and 6 weeks (end of 2-week post intervention period) assessing pain severity, self-efficacy and catastrophizing, physical function, opioid use, and quality of life outcomes. (Appendices P, Q, R) End-of-intervention interview (4 weeks) assessing usability and acceptability (Appendix T)
	• Wedical Record Abstraction (Appendix O)

 Table 1. Brief description of pilot cohort activities

PILOT COHORT:

The first few patients (up to 5) will onboard to the application and their involvement/feedback will focus on making final revisions to the mobile application and study procedures. All procedures will be the same for the 15 patients, however, data for the initial patients (up to 5) will not be included in final analysis as their involvement will be focused on revising final app bugs/iterations and modifications to study procedures before the pilot trial initiation. The following patients (up to 10) will be considered as the core pilot study participants to evaluate feasibility and acceptability of the application and study procedures.

Survey assessments

An RA will ask the patient to complete a baseline survey assessment after consenting, at the end of the 4-week intervention study period, and at the end of the 2-week post intervention period to assess key outcomes (pain severity/interference,⁴² QOL⁴³), potential mediators of intervention effects (catastrophizing⁴⁴, self-efficacy⁴⁵, perceived stress⁴⁶, anxiety/depression⁴⁷, sleep⁴⁸), acceptability,⁴⁹ and usability⁵⁰. The survey can be completed remotely though a link to a Partners Healthcare compliant electronic survey system (e.g. REDCap), over the phone with the RA, over Zoom with the RA,

in person with pen and paper or on a tablet. The Baseline survey will assess socio-demographics, barriers to pain management, pain severity, opioid use, pain and psychological symptoms, and quality of life, with metrics shown in Table 5. End of 4-week intervention period survey will largely replicate the baseline survey; additionally, patients will rate their satisfaction with STAMP+CBT using the 6-item Acceptability E-scale. Surveys will be used to assess pain and psychological symptom trajectory, medication use, and quality of life. See **Appendix P** for the Baseline survey items, **Appendix Q** for 4-week (end of 4-week intervention period) survey items, and **Appendix R** for 2-week (post intervention period) follow-up survey items. Additionally, a subset of patients (up to 10) will be invited for a qualitative interview focused on study burden, facilitators/barriers to app use, satisfaction, and perceived utility in order to guide future refinements to the app (see Appendix T) when they complete use of the app at 4 weeks (end of intervention study period).

Intervention

After the patient completes the baseline survey, the RA will meet with the patient (in person or virtually), to assist in either 1) downloading the application onto participants' mobile device or 2) providing/mailing the study phone to the participant. The RA will help to register the patient to the app and help set up any preferences. The RA will then conduct a 15-minute tutorial on the STAMP+CBT app and its intended use (Appendix S). The RA will also input the patient's pain medications from Epic, reconciling this list with the patient, and with the nurse navigator on the patient's care team if there are any discrepancies. As the nurse navigator is already a member of the care team, they'll have access to all Epic records and any documentation for this study included in Epic. The participant will also input their desired goal to work towards for the duration of the trial. During the trial, there is also a function in the app that allows participants to notify the research team if a medication or goal needs to be changed and reflected in the app. Final iterations to the app, research portal, and study procedures will be made following the initial few patients (up to 5) recruited to using the application. Thereafter, we will begin recruiting patients (up to 10) for the pilot study cohort.

Participants will utilize STAMP+CBT for 4-weeks (intervention study period). The 4 weeks will consist of all content introductions. Patients will also be offered the opportunity to continue their app use for the next 2 weeks (post-intervention period) until study completion (2 week follow up and survey), this will allow us to assess feasibility and acceptability of the appropriate length of use for the intervention. STAMP+CBT hosts and organizes patients' opioid/non-opioid analgesics. It has an extensive multi-media library of education content related to pain management (Appendix C)

and pain specific CBT concepts (Appendices C, D, and F). Content will be delivered on a schedule to ensure that patients receive all pain CBT and medication education available (Appendix U). STAMP+CBT prompts patients to take daily surveys for reporting of pain, pain catastrophizing, mood, opioid/pain medication use, and sleep symptoms and progress towards individualized goals (Appendix U). At the end of each survey, patients receive feedback according to their symptom severity, with links to tailored educational content about pain and psychological symptom management. (Appendix U). Patients also complete weekly surveys for reporting symptoms listed above as well as goal progress. If patients report any severe symptoms, they are instructed to contact their care team immediately, with a telephone number included on the application screen, see table 2, or to go the Emergency room/call 911 for a true medical emergency. If patients' pain is poorly controlled but not severe enough to be prompted to immediately contact their care team (for example if their average pain is above a 4 and not acceptable), they are reminded to contact their care teams if their symptoms worsen or they are concerned about it.

One protocol-mandated study staff outreach to patients will occur within a week of enrollment. An RA will call to assess any technical or usability problems with the app (e.g. how to access the app on their phone, where to find certain study areas, etc.). These technical discussions will be optional for the patient and more can be scheduled if requested. Thereafter, the RA will monitor the STAMP+CBT dashboard twice daily (Mon-Fri), for any patient reported severe symptoms (Table 2). If a patient reports one of these severe symptoms, the RA will contact the patient's nurse through a secure EPIC message to notify the patient's care team. Additionally, to assist in population management, a *tiered system notifications*, in the portal will indicate symptom severity, need for outreach and/or management changes (See Table 3). As an additional safety measure, the application always prompts the patients to contact their care team for any severe symptoms they report and there is no expectation for proactive clinician outreach. These procedures have been approved by participating clinic nurses. The application provides a direct link to call the Outpatient Palliative Care Clinic at DFCI.

To minimize the burden of the intervention on clinicians, there are no automated clinician alerts (i.e. email or in-basket message) for severe symptoms, rather, patients are prompted to call their care teams or 911 (emergency services) if they report severe symptoms (Table 2 and 3). Patients are reminded frequently throughout the application that the research portal is not monitored around the clock and therefore they should reach out for urgent needs. Reports (with summarized pain and psychological symptoms; opioid use data; side effects; patients' goals and reported goal attainment) will be sent to nurse managers, palliative care providers, and

oncologists to enable effective communication, opioid titration, and other management changes when prompted by the patient.

During the study patients will be asked to complete 3 survey assessments, one at baseline, one at the end of the 4-week intervention period, and another at the end of the 2-week post intervention period. Patients will also be invited to complete a short semi-structured interview about their experiences using the application (See Appendix T). See below for description of the surveys (Table 5).

Pain	• Worst pain = 9-10
	• Worst pain = 7-10 and new pain
Red Flag	Severe weakness or fatigue
Symptoms	• Lightheadedness or feeling like I was going to pass out
	• No gas or stool from my bottom (or ostomy) in the last
	2 days
	• Vomiting 2 or more times in the last 24 hours
	• Fever of 100.5 or greater
	• New or worsening chest pain
	• New or worsening shortness of breath
	New or worsening back pain
	• New numbness and weakness in one or both of your
	legs
	• Severe difficulty eating or drinking
	Hallucinations/nightmares
Opioid Side	Hallucinations
Effects	

Table 2. Severe Symptoms

Relief with opioids	No relief
	OK
	Unsure
	Good relief
Pain Control	Poor
	Suboptimal
	Good
Other Severe Symptoms	Number of severe symptoms on Table 2
	shown in red
Opioids need updating	Yes
	No
Mood	IF Patient responds to mood questions 17-
	20 with a total score of ≥ 12 : Low Mood
	IF Patient responds to mood questions 17-
	20 with a total score of <12: High Mood
Catastrophizing	IF Patient responses to catastrophizing
	questions 12-16 with a total score greater
	than ≥ 10 : High Stress
	IF Patient answers catastrophizing items
	12-16 with a total score <10: Low Stress
Sleep	If sleep item 23 on the survey score ≥ 3 :
	Poor
	If score <3: Good
Goals need updating	IF Patient answers "No, it needs to be
	changed" in goal-setting section of weekly
	survey: Goal needs updating

 Table 3: Report on Research Dashboard Based on Patient Responses

*Note: The RA will check the portal twice daily and send an EPIC message to the patient's nurse for all responses in red needing urgent evaluation

Chart Abstraction

The study team will complete a limited structured chart abstraction at baseline and at end-of-study to collect basic non-identifiable clinical/demographic information (See appendix O). Chart abstraction will assess clinical actions responding to STAMP+CBT data and healthcare utilization related to pain and symptom management (e.g. hospitalization, ER visits, urgent clinic visits for symptom management, psychosocial oncology social work, psychology, or psychiatry visits). As people with cancer have variable prognoses, they may pass away during a study; therefore, we want to be able to abstract and record if/when a patient passes away during or recently after their involvement. Should this situation arise, it can negatively influence outcomes of the study evaluation (feasibility/acceptability).

Chart Abstraction Information collected will include the following:

- **Demographics:** Gender, age, ethnicity, race
- **Cancer**: Patient's date of diagnosis, diagnosis (cancer type), stage at diagnosis, status of active curative or palliative treatment, history and date of surgery related to cancer, and whether patient has seen palliative care (yes/no)
- **Pain**: patient's last pain rating, type of pain, location of pain, surgeries or operations for pain, documented calls about pain.
- **Prescribed Pain Medicines**: Patient's prescribed short-acting opioid, long-acting opioid, and non-opioid pain medications, and length of time taking opioids.
- **Prescribed Anxiolytics**: Patients' prescribed anxiolytics and whether this was prescribed before or during the study
- **Prescribed Antidepressants**: Patients' prescribed antidepressants and whether this was prescribed before or during the study
- Medication/Opioid side effects: Constipation or related symptoms.
- **Clinic visits**: Unplanned or urgent clinic visits that include pain 6 months prior, during, and 6 months post-intervention, and social work, psychology, or psychiatry visits during study period
- **Mental Health Diagnoses**: Whether the patient has a mental health diagnosis and what mental health diagnosis the patient has.

Fable 4: Summary of developed STAMP+CBT content (See Appendix F for furthe	r
lescriptions):	

CBT for pain Modules	Location of Content	Type of Content	
Adaptive surveys: Depression, stress, anxiety, catastrophizing, sleep, personalized goals	Appendix B	Survey items	
Text or audio-visual content: Appendix C:			
Pain psychoeducation	Appendix C Appendix D	Written content Video content	
Emotional awareness	Appendix C	Written content	
Relaxation/ deep breathing	Appendix C	Written content	
Stress and pain	Appendix C	Written content	
Cognitive processes/restructuring for pain	Appendix C Appendix D	Written content Video content Behavioral Game: http://18.210.82.141/v31/	
Goal setting	Appendix C	Written content	
Activity setting	Appendix C Appendix D	Written content Video content	
Opioid Education	Appendix C Appendix D	Written content Video content	
Non-opioid analgesics education	Appendix C	Written content	

Human Subjects Research Category (NHSR, exempt, expedited, full review):

Pilot Cohort: Expedited

Human subjects research designation for the Pilot Cohort is **expedited**.

Informed Consent: Written consent will be obtained from all participants (Appendix AD). After identifying potential eligible patients, we will contact the treating physician via email or phone to request permission to approach any patient. If the physician approves the approach, we will ask them to introduce the study to the patient at a regularly scheduled visit and ask permission for the research team to contact them to further explain the study and offer participation. If the physician denies approach, we will not approach the patient to offer study participation.

After a clinician has approved the study team to approach their patient, the patients may be approached in person during an upcoming clinic visit. Once approached, the RA will review the study letter and consent form with the patient (Appendices X and AD). The study letter will notify participants that engagement in the study is completely voluntary and can be stopped at any

time for any reason. The palliative care clinic in which patients are being recruited for this study have also largely remained remote with tele-health services. Few patients attend in-person clinic appointment for palliative care outpatient care. Therefore, if approaching patients at the clinic is not possible, eligible patients may be approached remotely via phone. If a patient is contacted by phone, the RA will send the study letter and consent forms through a secure and personalized link in the FDA and HSSH compliant Mass General Brigham/Partners REDCap database. The RA will attempt to contact a patient three times. If contact is not established, the RA will email a copy of the recruitment letter to introduce the study (Appendix AC). The letter encourages the patient to contact the research team if they are interested in participating in the study. If the patient then contacts the research team, the study letter and consent form will be reviewed with the patient before obtaining written consent. If the patient does not respond by email or if they opt of the study participation, they will no longer be contacted. To account for patient understanding, the study letter will also be included in the app for review at any time.

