- 11.2 Statistical analyses will be utilized in the pilot intervention portion of this study to ascertain feasibility and acceptability. We will measure time spent on the app per day and per week, completion rates for surveys and content review, and frequency of log-ons over the course of the pilot. The primary objective is to determine feasibility and acceptability of STAMP+CBT. Defined using precision analysis, we will consider the intervention to be feasible if >70% of subjects complete \geq 4 of the 6 pain-CBT modules and patients will complete 50% of surveys by the end of 4-weeks (completion of the 4-week intervention study period and completion of the 2-week post intervention period).^{40,41} A module will be considered complete if the participant engages in >70% of its content, including completing mHealth survey items, psycho-educational content, and app exercises. The intervention will be considered acceptable if >80% of the acceptability items are rated 4 or higher/5; lower ratings will lead to app refinements. Other feasibility measures will assess time to accrual, participation rates, and study retention and completion rates. Power calculation: With 10 patients, we will be able to estimate these proportions with margins of error (half of a 95% confidence

interval) of approximately 18% or less assuming that the feasibility threshold of 70% is reached. This margin of error is small enough so that proportion estimates relevant to study feasibility will be accurate and provide informative guidance for future, larger studies. Although power is not sufficient in this pilot, we will explore associations between levels of engagement and changes in pain severity/interference, opioid use, catastrophizing, sleep, mood, and pain self-efficacy.

- 11.3 The data the research team will access regarding app utilization will include; date and time of app log-ins, date of time of survey completion, survey responses, including clinical reporting of daily symptoms and medication usage, total app log-ins during intervention period, percent of surveys completed during intervention period, date time and frequency patients access external educational content.
- 11.4 PHI data will be collected using REDCap and the STAMP+CBT app.

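### The primary feasibility rule is stated twice with different windows: section 8.1 makes weeks 5–6 exploratory, section 11.2 puts them inside the criterion

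*Combined protocol and SAP*

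**What the plan says.** The rule for declaring feasibility, the primary outcome, appears in two places.

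- **Section 8.1 (Endpoint 1):** "feasible if >70% of subjects complete >4 of the 6 pain-CBT modules and completes 50% of surveys by the end of 4 weeks". The parenthesis that follows names the 4-week intervention period and then says "completion of the 2-week post intervention period will be exploratory". The number of patients who go on reviewing app content in weeks 5–6 is listed separately, among the other feasibility measures.
- **Section 11.2 (statistical analyses):** more than 70% of subjects must "complete \geq 4 of the 6 pain-CBT modules and patients will complete 50% of surveys by the end of 4-weeks". The parenthesis that follows reads "completion of the 4-week intervention study period and completion of the 2-week post intervention period". The word exploratory is absent.

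Other sections bear on the window:

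- **Section 7.0** gives 4 weeks as the total period of app use, within 6 weeks on study.
- **Section 11.3** lists, among the data to be accessed, "percent of surveys completed during intervention period".
- **Section 9.2** has patients pilot the app for 4 weeks, "or 6 weeks if they request to review the content further". **Table 1** has "extended 2 weeks for review of content if patient's request this". **Section 9.3, Intervention**, says "Patients will also be offered the opportunity to continue their app use for the next 2 weeks".

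No section says which statement of the rule governs.

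**The concern.** A decision rule needs one data cut. Section 8.1 sets it at week 4. Section 11.2 names week 4 and then extends the criterion to a period that ends at week 6. An analyst who works from 11.2 could count app activity up to week 6; one who works from 8.1 could not. Since patients may use the app after week 4, the two counts need not agree.

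With about 10 patients in the analysis, a change in one patient's status can reverse the conclusion. If both statements remain, the choice between them can be made after the results are known.

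The two statements also differ, as supplied, in the module cut-off: more than 4 of 6 in 8.1, at least 4 of 6 in 11.2. This could affect the verdict too, but only if the symbol in 8.1 is what the sponsor wrote.

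**Working it through.** **Plan's own figure.** The only computed figure attached to the rule is the margin of error of about 18% with 10 patients at 70%. The usual formula gives 1.96 × √(0.7 × 0.3 / 10) = 0.284, or 28 points, so it does not reproduce. That is a separate matter, and nothing below uses it.

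**Step 1. The two windows side by side.**

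| | Section 8.1 | Section 11.2 |
|---|---|---|
| Time limit | end of 4 weeks | end of 4 weeks |
| 4-week period | in the criterion | in the criterion |
| 2-week post-intervention period | exploratory | in the parenthesis, not marked exploratory |

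The last row differs in words, so a symbol misread from the PDF cannot explain it.

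**Step 2. Can the difference matter?** Section 11.2 counts a module as complete when the patient has engaged in more than 70% of its content. Sections 9.2 and 9.3 and Table 1 let patients return to content in weeks 5–6. A patient just short on a module at week 4 can therefore pass that mark later. The survey condition is less exposed, because 11.3 ties survey completion to the intervention period.

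**Step 3. How many patients decide it?** Take 10 analysed patients (the figure in 8.1 and 11.2). 7/10 = 70% is not more than 70%; 8/10 = 80% is. The bar is 8. With 7 qualifying at week 4, one more in weeks 5–6 changes the verdict from not feasible to feasible. Section 9.3 says up to 10, so fewer are possible. With 9 patients the bar is 7 (7/9 = 77.8%; 6/9 = 66.7%), and with 8 it is 6 (6/8 = 75%; 5/8 = 62.5%). One patient is still enough at the boundary. The documents give no basis for a probability of this happening.

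**Step 4. Module cut-off, only if the source PDF confirms more than 4 in section 8.1.** More than 4 of 6 means 5 or 6 modules; at least 4 means 4, 5 or 6. A patient with exactly 4 fails one version and passes the other. Suppose all 10 patients meet the survey condition:

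- Modules 6, 6, 5, 5, 5, 5, 4, 4, 3, 2: 8/10 have at least 4 (feasible), 6/10 have more than 4 (not feasible).
- Modules 6, 6, 6, 5, 5, 5, 5, 5, 3, 2: 8/10 under both, so the verdicts agree.

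To see how often the verdicts would differ, let q be the chance that a patient completes a given module and ρ the within-patient correlation. Both are assumptions; the documents give neither. Modules completed per patient follow Binomial(6, q) when ρ = 0, otherwise a beta-binomial with a = q(1/ρ − 1) and b = (1 − q)(1/ρ − 1). Every patient who passes the stricter cut-off passes the looser one, so

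P(verdicts differ) = P(Bin(10, P[≥4]) ≥ 8) − P(Bin(10, P[≥5]) ≥ 8).

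Example with q = 0.80 and ρ = 0: P[≥4] = 0.901 and P[≥5] = 0.655. The chance of at least 8 of 10 is 0.932 and 0.273, a difference of 0.658.

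| q | ρ = 0 | ρ = 0.3 | ρ = 0.5 | ρ = 0.7 |
|---|---|---|---|---|
| 0.50 | 0.4% | 1.7% | 2.3% | 2.3% |
| 0.60 | 9.3% | 9.3% | 8.5% | 6.4% |
| 0.70 | 49.1% | 26.3% | 18.8% | 11.7% |
| 0.75 | 68.5% | 34.2% | 22.7% | 13.2% |
| 0.80 | 65.8% | 36.0% | 22.9% | 12.5% |
| 0.85 | 38.4% | 28.6% | 18.0% | 9.4% |
| 0.90 | 9.6% | 14.6% | 9.5% | 4.8% |
| 0.95 | 0.4% | 2.9% | 2.0% | 1.0% |

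At these values the range is about 0.4% to 68%.

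**Step 5. Same subject or not?** In 8.1 the module and survey conditions read as one requirement on each subject. In 11.2 the survey condition has its own subject and can be read as a separate requirement on the group.

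**The case against.** The strongest reply is that the documents largely settle the window. Both sections use week 4 as the operative limit. Section 8.1 labels the later period exploratory, 7.0 gives 4 weeks of app use, 11.3 counts surveys within the intervention period, and 9.2 and Table 1 describe the extension as review on request. This is also a single-arm pilot with no hypothesis test, and 8.2 draws its conclusion from qualitative and quantitative results together. All of that stands. It makes a slip in 11.2 the likely explanation and keeps the point small. It does not remove the conflict, because 11.2 is the analysis section and content can still be completed after week 4.

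Three stronger readings are tempting, and the documents do not support them.

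- *A reader might infer that the sponsor set two different module cut-offs.* The two sentences are near copies, with the same citations and the same text around them. The symbol in 8.1 may have lost its bar in PDF reading. The at-least sign does survive elsewhere, for example in the eligibility criteria, so the supplied text cannot decide the matter either way.
- *A reader might take the upper end of the table as the expected rate of conflict.* It depends on that unconfirmed symbol and on assumed inputs, and the lower end is negligible.
- *A reader might infer that 11.2 makes completing week 6 a condition of success*, so that 8/10 could fall to 7/10 through a late loss. That contradicts 11.2's own four-week limit.

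**Conclusion.** The rule is wrong as written in one respect that is certain: 11.2 includes the 2-week post-intervention period in the feasibility criterion, while 8.1 makes it exploratory and both name week 4 as the limit. The size is one patient at the boundary, 7/10 against 8/10 if 10 are analysed. For this to happen, a patient just short at week 4 must complete more content in weeks 5–6, which the plan allows but does not quantify.

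The module cut-off is secondary and unproven. If the source PDF shows at least 4 in 8.1, that difference disappears and the table with it. If it shows more than 4, patients with exactly 4 modules can decide the verdict, at a rate that could be trivial or large and depends on completion rates the documents do not give.

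Severity: minor. It is a small, probably accidental discrepancy, worth correcting because it sits in the primary decision rule.

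**What to change.** Before any analysis:

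1. Put one identical rule in sections 8.1 and 11.2, with a week-4 data cut for every patient.
2. In 11.2, delete the 2-week clause from the parenthesis or mark it exploratory, as 8.1 does.
3. Use 8.1's construction in both sections, so that the same subject must meet the module and the survey condition.
4. Check the symbol in 8.1 against the source PDF. If it does read more than 4, the sponsor should choose one cut-off (at least 4 or at least 5 of 6) and use it in both sections.

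The cost is a wording amendment to two sections. It needs no extra patients, visits or data.
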